14.3.15 Changes in level of disability as measured by EDSS

The Expanded Disability Status Scale (EDSS) ranges from 0 to 10 in increments of 0.5 on an ordinal scale. Higher scores represent a higher level of disability. Details of the EDSS scoring are included in the appendix of the study protocol.

The observed EDSS and the change from Baseline will be presented by Visits using summary statistics (median, quartiles, min, max) and by the following categorization for each Visit:

- ≤ 3 ,
- $>3 - <6$,
- ≥ 6 .

Analysis (Analysis Set)	Derivation	Statistical Analysis Methods	Missing data handling
Secondary endpoint: Changes in level of disability as measured by EDSS at Month 6, 12, 18, and 24 compared to Baseline			
Tertiary (FAS)	Changes from Baseline of EDSS at Month i Visit, where i= 6, 12, 18 and 24.	Descriptive summary statistics for the median and quartiles.	

Tertiary (FAS)	EDSS categories (<3, 3-<6, ≥6) at Baseline, Month 6, 12, 18 and 24 Visits.	Descriptive summary statistics.	Missing values will be included in the denominator and presented as a separate category.
----------------	--	---------------------------------	--

14.3.16 Changes in level of disability as measured by 9HPT

The 9HPT should be completed at Baseline and then at Month 6, 12, 18, and 24 Visit to measure the level of disability over time. The subjects have to stick 9 pegs in 9 holes and place them back. That will be done twice for each hand. The mean of the 4 stop times will be analyzed. At least one stop time must be recorded, otherwise, the Visit will be considered as missing. Details of the 9HPT are included in the appendix of the study protocol.

Analysis (Analysis Set)	Derivation	Statistical Analysis Methods	Missing data handling
Tertiary endpoint: Changes in level of disability as measured by 9HPT at Month 6, 12, 18, and 24 Visit compared to Baseline			
Tertiary (FAS)	Change from Baseline in mean time of the 9HPT to the Month i Visit, where i= 6, 12, 18, and 24.	Mixed-effects linear model for repeated measures, same as in Tertiary Analysis for Change from Baseline in CUA lesion count (see Section 14.3.1)	Same as in Tertiary Analysis for Change from Baseline in CUA lesion count (see Section 14.3.1)

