12.6 Appendix 6: 9-Hole Peg Test (9HPT)

General Information:

- The 9HPT should be conducted with the dominant arm first
- One practice trial (per arm) should be provided prior to timing the test
- Timing should be performed with a stopwatch and recorded in seconds
- The stop watch is started when the patient touches the first peg
- The stop watch is stopped when the patient places the last peg in the container

Set-up (Mathiowetz et al, 1985):

- A square board with 9 holes,
 - holes are spaced 3.2 cm (1.25 inches) apart
 - each hole is 1.3 cm (0.5 inches) deep
- 9 wooden pegs should be .64 cm (.25 inches) in diameter and 3.2 cm (1.25 inches) long
- A container that is constructed from .7 cm (.25 inches) of plywood, sides are attached (13 cm x 13 cm) using nails and glue
- The peg board should have a mechanism to decrease slippage. Self-adhesive bathtub appliques were used in the trial
- The pegboard should be placed in front of the patient, with the container holding the pegs on the side of the dominant hand

Patient Instructions (Mathiowetz et al, 1985):

- The instructions should be provided while the activity is demonstrated
- The patient's dominant arm is tested first
- Instruct the patient to:
 - "Pick up the pegs one at a time, using your right (or left) hand only and put them into the holes in any order until the holes are all filled. Then remove the pegs one at a time and return them to the container. Stabilize the peg board with your left (or right) hand. This is a practice test. See how fast you can put all the pegs in and take them out again. Are you ready? Go!"

- After the patient performs the practice trial, instruct the patient:
 - “This will be the actual test. The instructions are the same. Work as quickly as you can. Are you ready? Go!” (Start the stop watch when the patient touches the first peg.)
 - While the patient is performing the test say “Faster”
 - When the patient places the last peg on the board, instruct the patient “Out again...faster.”
 - Stop the stop watch when the last peg hits the container.
- Place the container on the opposite side of the pegboard and repeat the instructions with the non-dominant hand.

Dominant Hand (circle one): Right Left Time to complete the test in seconds:

Date: _____ Dominant Hand: _____ Non-Dominant Hand: _____

Date: _____ Dominant Hand: _____ Non-Dominant Hand: _____

Date: _____ Dominant Hand: _____ Non-Dominant Hand: _____

Date: _____ Dominant Hand: _____ Non-Dominant Hand: _____

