- 1 year = 365.25 days.

Time window

- Day 1 is the day of start of study medication, the day before is Day - 1 (no Day 0 is defined),
- Study day / Treatment day is defined relative to Day 1.

The Visit schedule is defined as follows:

- 1 month = 30 days,
- 1 year = 360 days,

relative to the start date of the Baseline Visit for Treatment Course 1 and relative to the start date of the Month 12b Visit as defined in the eCRF (see also Section 15.3) for Treatment Course 2.

In each analysis, should assessments be delayed, subjects' assessment data will be treated as though it occurred at the time point specified (i.e., out of Visit windows will be not excluded or adjusted for any analyses) and inferences will be conducted accordingly. Thus, further time windows will not be specified.

All observations from unscheduled Visits will be included only in the analyses of Visit independent summaries (e.g. counts of events, progressions or worst value during Treatment Period) unless for the unscheduled Visits prior to start of study medication and the last assessment available. In case of unscheduled Visits prior to start of study medication, these will be considered to define Baseline. In the last missing case the ET Visit will be imputed by the unscheduled Visit.

The assessments of the ET Visit will be mapped to the nearest planned post-Baseline Visit with a missing assessment before or after the ET Visit of the individual assessment for all statistical analyses and descriptive summaries. As not all assessments of the ET are performed at each Visit, the different assessments of the ET can be assigned to different Visits. If the duration (in days) between the ET Visits and two missing planned Visits are equal, then the assessment will be assigned to the later Visit.

Handling of missing data

Unless otherwise specified in respective sections, missing data will not be replaced.

The handling of missing covariate and stratification factor information is described below.

The handling of missing DMD end date is described in Section 12.

Incomplete or missing onset dates of relapses from "MS Relapse Report" will be imputed as follows:

- In cases where the onset date is partially missing but the onset month and year, or the onset year are equal to the start of study medication or the date is missing then the onset date will be replaced by the start date of study medication.

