14.3.13 No Evidence of Progression or Active Disease

No Evidence of Progression or Active Disease (NEPAD) is a composite measure, evolution of NEDA-3, including relapses and different measurements of disability progression and MRI activity.

NEPAD at Month 24 is defined as the composite endpoint of NEDA-3 and the absence of:

CCI [REDACTED]

CCI [REDACTED]

- 20% progression on T25-FW,
- 20% progression on 9HPT,

during the Treatment Period.

20% confirmed T25FW progression

20% confirmed progression on T25FW is defined by an increase of at least 20% from T25FW Baseline that is sustained over a 6-month time Period.

The increase will be defined as sustained when it occurs on two post-Baseline Visits, which are at least 166 days (6 months * 30 -14 days Visit Window) apart and no score at any other Visit including unscheduled Visits in between is less than the defined increase.

The occurrence of a 20% confirmed T25FW progression is defined as:

- Yes: sustained T25FW progression that started during the Treatment Period.
- No: at least 2 post-Baseline T25FW assessments that are 166 (or more) days apart are available and no sustained T25FW progression that started during the Treatment Period.
- Unknown: Otherwise.

Only T25FW assessments with the same assistance devices as at Baseline will be analyzed. T25FW trials which couldn't be finished by the subjects will be imputed with 3 minutes (see Section 14.3.17).

20% confirmed 9HPT progression

20% confirmed progression on 9HPT is defined by an increase of at least 20% from 9HPT Baseline that is sustained over a 6-month time Period.

The increase will be defined as sustained when it occurs on two post-Baseline Visits, which are at least 166 days (6 months * 30 - 14 days Visit Window) apart and no score at any other Visit including unscheduled Visits in between is less than the defined increase.

The occurrence of a 20% confirmed 9HPT progression is defined as:

- Yes: sustained 9HPT progression that started during the Treatment Period.
- No: at least 2 post-Baseline 9HPT assessments that are 166 (or more) days apart and no sustained 9HPT progression that started during the Treatment Period.
- Unknown: Otherwise.

Analysis of NEPAD

NEPAD will be analyzed with a logistic regression with adjusting factors age (in years) and EDSS at Baseline (≤ 3 , >3).

Analysis (Analysis Set)	Derivation	Statistical Analysis Methods	Missing data handling
Tertiary endpoint: NEPAD at 24 months			

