14.3.17 Changes in level of disability as measured by T25FW

T25FW is a quantitative mobility and leg function performance test based on a timed walk over 25 feet (approximately 7.6 meters). Administration time will vary depending upon the ability of the subject. Subjects have to twice walk a trial of 25 feet. The time limit for each trial is 3 minutes. At least one trial has to be completed to calculate the mean time for a Visit. If the subjects couldn't finish a trial, the trial will be scored with 3 minutes. T25FW performed with a different assistance device as compared to what was used at Baseline will be considered as "changed device" and will not be included in the statistical analysis. Details of the T25FW are included in the appendix of the study protocol.

Analysis (Analysis Set)	Derivation	Statistical Analysis Methods	Missing data handling
Tertiary endpoint: Changes in level of disability as measured by T25FW at Month 6, 12, 18, and 24 Visit compared to Baseline			
Tertiary (FAS)	Change from Baseline in mean time of the T25FW to the Month i Visit, where i= 6, 12, 18, and 24.	Mixed-effects linear model for repeated measures, same as in Tertiary Analysis for Change from Baseline in CUA lesion count (see Section 14.3.1)	Same as in Tertiary Analysis for Change from Baseline in CUA lesion count (see Section 14.3.1)

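### The 9HPT visit score accepts a single stop time from either hand and has no rule for an unfinished attempt, so losing a hand carries no penalty and can look like improvement

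*SAP*

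**What the plan says.** **Scoring.** SAP 14.3.16 has the subject place and remove the pegs, and says: "That will be done twice for each hand". The analysis variable is then fixed: "The mean of the 4 stop times will be analyzed". A visit is scored unless no time at all exists: "At least one stop time must be recorded, otherwise, the Visit will be considered as missing". The change from Baseline in this mean goes into a repeated-measures mixed model at Months 6, 12, 18 and 24.

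**Missing data.** The general rule in SAP Section 9 is: "Unless otherwise specified in respective sections, missing data will not be replaced". SAP 14.3.16 specifies nothing different.

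**Progression.** In SAP 14.3.13, "20% confirmed progression on 9HPT is defined by an increase of at least 20% from 9HPT Baseline", held for six months. It must be seen at two post-Baseline visits at least 166 days apart, with no lower score in between. The answer is No once two assessments that far apart exist without such an increase, and Unknown otherwise.

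**Sister test.** For T25FW, SAP 14.3.17 says: "If the subjects couldn't finish a trial, the trial will be scored with 3 minutes". SAP 14.3.13 repeats this for T25FW. Neither section has a counterpart for 9HPT.

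**Protocol.** Appendix 6 stops the watch only once the last peg is back in the container. It gives no time limit, maximum score or inability code, and Section 7.3.2.3 adds none. It also says: "One practice trial (per arm) should be provided prior to timing the test". It then describes one actual test per hand, and its form has one time per hand per date.

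**The concern.** A hand that cannot finish produces no stop time. Under a rule satisfied by one time from either hand, the visit is still scored, and the score then measures something different from Baseline: one hand instead of two. The T25FW trials repeat the same task, so dropping one loses precision. The 9HPT times come from two different hands, so dropping one hand changes the quantity.

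Two results are at stake. In the mixed model, the mean time can move towards stability or benefit when function has been lost. In the NEPAD component, the visit counts as an observed assessment. It can therefore support a No, or interrupt a progression that was being confirmed, and neither the Unknown category nor the model's handling of missing data comes into play.

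**Working it through.** The plan states no figure here, so there is none to reproduce.

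**Inputs from the documents**
- Two attempts per hand, one mean over all times, one time sufficient (SAP 14.3.16).
- No replacement (SAP Section 9).
- No stop time without completion (protocol Appendix 6).
- Progression at +20%, confirmed at least 166 days later (SAP 14.3.13).

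**Assumed inputs.** The documents give no hand times. I take a better hand of g = 20 s that stays at 20 s, and a worse hand of w = 20 to 40 s at Baseline.

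**Slower hand lost.** Baseline B = (2g + 2w)/4 = (g + w)/2. With neither slower-hand attempt finished, the recorded times average g. Change = 100 × (g − B)/B.

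| w (s) | B (s) | Visit score (s) | Change |
|---|---|---|---|
| 20 | 20.0 | 20.0 | 0% |
| 22 | 21.0 | 20.0 | −1.0/21.0 = −4.8% |
| 25 | 22.5 | 20.0 | −2.5/22.5 = −11.1% |
| 30 | 25.0 | 20.0 | −5.0/25.0 = −20.0% |
| 40 | 30.0 | 20.0 | −10.0/30.0 = −33.3% |

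With one timed trial per hand, as in Appendix 6, B is again (g + w)/2, so the table does not depend on which document is followed.

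**Other cases, with 20/30 s at Baseline (B = 25 s)**
- Faster hand lost: score 30 s, (30 − 25)/25 = +20%.
- One of two slower-hand attempts fails: (20 + 20 + 30)/3 = 23.3 s, −6.7%.
- Slower hand slows to 60 s but finishes: (2 × 20 + 2 × 60)/4 = 40 s, +60%. Partial loss therefore scores worse than total loss.
- Slower hand lost and the better hand also slows: the score still shows improvement until the better hand passes 25 s (25% slower). It reaches the threshold of 1.2 × 25 = 30 s only when that hand is 50% slower.
- Only the better hand timed at Baseline, both hands later: 20 s becomes 25 s, +25%. The mismatch can also run the other way.

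**Effect on confirmation.** Take the same 20/30 s subject with 40 s at Month 6, above the 30 s threshold. At Month 12 the slower hand cannot finish and the score is 20 s. Month 12 does not confirm the Month 6 increase. Because 20 s lies below the threshold, it also blocks confirmation of Month 6 by any later visit.

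**The case against.** **The rule is inferred.** The SAP refers to the mean of four times and never says the mean of whatever times exist. That is correct, and a reader should not take the second wording as the SAP's own. But a visit with one to three times is declared non-missing, nothing is replaced, and no other scoring is offered. Likewise, 14.3.13 does not say which 9HPT score its 20% applies to; the two-hand mean is the only score defined.

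**Improvement is not automatic.** A reader might infer that losing a hand always looks like benefit. It does so only if the lost hand was slower at Baseline and the other hand stays below the Baseline two-hand mean. What holds generally is that the failure itself adds nothing to the score.

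**NEPAD has other safeguards.** A reader might infer that these subjects are wrongly classed as free of progression. The documents do not support that as a rule. NEPAD requires NEDA-3, so a qualifying relapse, confirmed EDSS progression or MRI activity already makes it fail, and part of its definition is redacted. Protocol Appendix 7 grades severe monoparesis as pyramidal 3 and monoplegia as 4, which Appendix 8 places at about EDSS 3.0 and 4.0. From a low Baseline EDSS, sustained loss of a hand would often meet the EDSS component. The exposure lies mainly at higher Baseline EDSS.

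**T25FW is an imperfect model.** SAP 14.3.17 also needs at least one completed trial before a mean is calculated, so a subject who finishes neither walk may be missing and not scored at 3 minutes. It shows that the unfinished-attempt problem was recognised, not that the T25FW rule can simply be copied.

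**Such cases may be few.** Entry requires EDSS of 5.0 or less, and the documents give no frequency. An eCRF guide might hold an inability code, but the SAP would still have to say how to score it.

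**Conclusion.** The concern holds as a gap in the scoring rule. As written, SAP 14.3.16 lets a one-hand visit be compared with a two-hand Baseline and gives inability no penalty. Under the assumed times, losing the slower hand changes the score by −4.8% to −33.3% for a worse hand of 22 to 40 s. The change is 0% for equal hands and +20% if the faster hand of a 20/30 s pair is lost. These are illustrations, and they rest on the available-times reading and a stable remaining hand.

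The effect is confined to tertiary, exploratory endpoints: the 9HPT change model and the 9HPT component of NEPAD. It does not reach the primary endpoint. How many subjects would be affected cannot be judged from the documents.

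**What to change.** 1. In SAP 14.3.16, replace the one-stop-time rule. Average within each hand, then average the two hands, and require at least one time per hand at Baseline and at the visit. Otherwise the mean time is missing in the mixed model. In the single-failed-attempt example above this gives (20 + 30)/2 = 25 s, a change of 0% instead of −6.7%.
2. In SAP 14.3.13, where the record shows that a hand completed the test at Baseline but could not at the visit, count that visit as meeting the 20% criterion. Do not apply this to a hand already unable at Baseline.
3. If a maximum time is wanted in the mixed model, state it in advance and present it as a sensitivity analysis. Capped values have high leverage on raw seconds. Borrowing the T25FW limit purely as an illustration, the 20/30 s subject scores (2 × 20 + 2 × 180)/4 = 100 s, or +300%; for w from 20 to 40 s the change runs from +400% to +233%.
4. Reconcile the SAP's two timed trials per hand with the single timed trial per hand in protocol Appendix 6. Until then, visits with fewer than four times could be routine.

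**Cost.** This is SAP wording and one derivation. 9HPT is not among the assessments listed for the Month 6 interim analysis (SAP 6.1, Table 1). Some visits become missing, and the model treats them as missing at random, which is doubtful when the cause is inability; the sensitivity analysis addresses that. The inability rule works only where the reason for a missing time was recorded, and neither Appendix 6 nor SAP 14.3.16 shows that it is.

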14.3.17 Changes in level of disability as measured by T25FW

T25FW is a quantitative mobility and leg function performance test based on a timed walk over 25 feet (approximately 7.6 meters). Administration time will vary depending upon the ability of the subject. Subjects have to twice walk a trial of 25 feet. The time limit for each trial is 3 minutes. At least one trial has to be completed to calculate the mean time for a Visit. If the subjects couldn't finish a trial, the trial will be scored with 3 minutes. T25FW performed with a different assistance device as compared to what was used at Baseline will be considered as "changed device" and will not be included in the statistical analysis. Details of the T25FW are included in the appendix of the study protocol.

Analysis (Analysis Set)	Derivation	Statistical Analysis Methods	Missing data handling
Tertiary endpoint: Changes in level of disability as measured by T25FW at Month 6, 12, 18, and 24 Visit compared to Baseline			
Tertiary (FAS)	Change from Baseline in mean time of the T25FW to the Month i Visit, where i= 6, 12, 18, and 24.	Mixed-effects linear model for repeated measures, same as in Tertiary Analysis for Change from Baseline in CUA lesion count (see Section 14.3.1)	Same as in Tertiary Analysis for Change from Baseline in CUA lesion count (see Section 14.3.1)

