7.3.2.4 Timed 25-Foot Walk (T25FW)

The T25FW is considered the best characterized objective measure of walking disability and can be used across a wide range of walking disabilities in MS. The subject is instructed to walk as fast and safely as possible (i.e., maximal walking speed) across a clearly marked, linear 25-foot or 7.62-m course. There are no turns in the course, and the T25FW starts with a static start (i.e., standing upright and still). The subject may use an assistive device. The subject is timed walking the 25-foot course twice, and T25FW score is the average in seconds of the two successive trials (Motl RW, 2017).

The T25FW should be completed at Pre-Baseline, Baseline and then at the end of Months 6, 12 18, and 24 to measure the level of disability over time.

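### T25FW scoring rule: read literally, failing one of two walking trials scores about 93 s but failing both gives no value, and SAP 14.3.13 states the rule differently

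*SAP*

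**What the plan says.** SAP 14.3.17 describes the test as two walks per visit: "Subjects have to twice walk a trial of 25 feet". It adds: "The time limit for each trial is 3 minutes". Two scoring rules follow. The first is "At least one trial has to be completed to calculate the mean time for a Visit". The second covers a subject who cannot finish a trial: "the trial will be scored with 3 minutes". Walks done with a different assistance device from the one used at Baseline "will not be included in the statistical analysis". The endpoint is the change from Baseline in mean time. It is analysed with the repeated-measures linear model of SAP 14.3.1, under which missing post-Baseline values are not imputed and are assumed missing at random.

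SAP 14.3.13 uses the same test for the 20% confirmed T25FW progression component of NEPAD. There, trials that could not "be finished by the subjects will be imputed with 3 minutes", with a cross-reference to 14.3.17 but without the condition that one trial be completed. Confirmed T25FW progression also has its own row in the analysis table of 14.3.13.

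Protocol 7.3.2.4 sets the unit: "T25FW score is the average in seconds of the two successive trials".

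**The concern.** The condition and the penalty work against each other. If *completed* means finished, the 180 s penalty reaches only subjects who can still finish one trial. Those who can finish neither have no visit mean. Their absence is caused by the outcome being measured, so missing at random is the wrong assumption for them, and the mean change is pulled towards no deterioration.

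For a subject with two unfinished trials, 14.3.17 read literally gives nothing, while 14.3.13 as written gives 180 s. Two programmers could each follow the SAP and report different T25FW progression results.

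The scale adds to this. Ordinary walking times are likely to be a few seconds, and values near 93 or 180 s enter a normal-theory model of raw seconds. The estimated mean change can then depend on one or two subjects.

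**Working it through.** The documents give no expected value, SD or power for T25FW, so there is no stated figure to reproduce.

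**Inputs from the documents:** two trials per visit, 180 s for an unfinished trial, the one-completed-trial condition and the raw-seconds linear model (SAP 14.3.17); missing at random (SAP 14.3.1); the 20% threshold and 166-day confirmation (SAP 14.3.13); 265 planned subjects (protocol synopsis).

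**Assumptions:** Baseline 6 s (range 4 to 20 s); SD of change among other subjects 2 s (range 1 to 4 s); the finished trial equals the Baseline time *b*.

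**1. Visit score.**
- One unfinished trial: (180 + 6)/2 = 93 s, a change of +87 s. The imputed value is 180/186 = 97% of the two-trial sum.
- In general the change is (180 − *b*)/2: +88 s at *b* = 4 and +80 s at *b* = 20.
- Two unfinished trials: no value under the literal 14.3.17 rule; 180 s and a change of +174 s under 14.3.13 as written.

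**2. Progression status.** One unfinished trial meets the 20% threshold at a visit when (180 + *b*)/2 ≥ 1.2*b*, that is for *b* ≤ 180/1.4 ≈ 129 s. Now take a subject with no delay to Treatment Course 2 and no change of device, who walks normally at Months 6 and 12 and finishes neither trial at Months 18 and 24.
- 14.3.13 as written: 180 s at both late visits, at least 166 days apart, so progression is Yes.
- 14.3.17 read literally: both late visits have no value. Months 6 and 12 are at least 166 days apart without progression, so the result is No.
- With one unfinished trial at each late visit, the result is Yes under both sections. The reversal of severity therefore reaches the binary row too.

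**3. Influence on the mean at one visit, N = 265.** √265 = 16.28.

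| | No failure | One partial failure (+87 s) | One total failure scored 180 s (+174 s) |
|---|---|---|---|
| Shift in mean | 0 | 87/265 = 0.33 s | 174/265 = 0.66 s |
| SD of change, SD 2 s | 2 | √(4 + 87²/265) = 5.7 | √(4 + 174²/265) = 10.9 |
| SE | 0.12 | 0.35 | 0.67 |

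At SDs of 1, 2 and 4 s the SE without the failure is 0.061, 0.123 and 0.246. The 0.33 s shift is then 5.3, 2.7 and 1.3 SEs. Three partial failures shift the mean by 3 × 87/265 = 0.98 s. The median hardly moves in any of these cases.

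**4. After the fix.** Scoring both unfinished trials as 180 s restores the order (+87 s, then +174 s) but doubles the outlier. The scale therefore has to change as well. On walking speed, taken per trial and averaged:
- Baseline: 25/6 = 4.17 ft/s. An unfinished trial: 25/180 = 0.14 ft/s.
- One failure: (4.17 + 0.14)/2 = 2.15, a change of −2.01. Two failures: 0.14, a change of −4.03. The order is kept.
- Shift in the mean from one total failure: 4.03/265 = 0.015 ft/s. A 2 s SD at 6 s corresponds roughly to 2 × 25/6² = 1.39 ft/s, so the SE is 1.39/16.28 = 0.085 and the shift is about 0.2 SE. In raw seconds it is 0.66/0.123 = 5.3 SEs.

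**The case against.** **The SAP never says that a visit with two unfinished trials is missing.** This is right. *Completed* is not defined. SAP 14.3.16 states outright that a 9HPT visit without a recorded time is missing, and 14.3.17 has no such sentence. One can read 14.3.17 as scoring any trial performed but unfinished at 180 s, with no mean only when the test was not done. The cross-reference in 14.3.13 supports that reading. The section also points to a protocol appendix on T25FW that is not readable in the public copy, so a definition there cannot be ruled out. A reader might infer that the plan definitely drops total walking loss. The text supports only that its literal wording does so and that the two sections need reconciling.

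**NEPAD would not change.** Largely right. Entry requires EDSS of at most 5.0. On the distance table in protocol Appendix 8, a subject who cannot finish 25 feet (about 7.6 m) scores at least 6.0. If that is sustained, it meets the EDSS progression definition and fails NEDA-3, and so NEPAD. A reader might infer that NEPAD depends on the T25FW reading, or that lost walking vanishes from the trial. Neither follows, since EDSS is analysed separately. What stands is the separate T25FW progression row.

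**Safeguards exist.** Protocol 8.5.1 says model assumptions will be examined, and 8.5.3 permits transformations or non-parametric methods. SAP Sections 9 and 14 already provide medians and quartiles by visit. But 14.3.17 names no alternative analysis, so the choice would be made after seeing the data, and no transformation supplies a value that the rule withholds.

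**Many who decline this far may be excluded for a new device anyway.** This is possible, and rescoring would not bring them back. It is a reason to report their number.

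**Conclusion.** The point holds as a defect in the scoring rule. Read literally, 14.3.17 penalises the lesser failure and gives no value for the greater one. 14.3.13 omits the condition, so confirmed T25FW progression can be Yes or No for the same subject.

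The effect on the mean depends on assumptions. At N = 265 and a 6 s Baseline, one partial failure shifts it by about 0.33 s. That is 1.3 to 5.3 SEs for SDs of change from 4 down to 1 s, and at 2 s the SE rises from about 0.12 to 0.35. A partial failure dominates that subject's own visit mean. It would be tempting to say that it makes the cohort result unusable, but the documents give no SD to support that.

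Impact is limited. The endpoint is tertiary, exploratory and uncorrected for multiplicity, and the EDSS entry limit makes such failures likely to be few. The change is still worth making because the rule can give a wrong result and is cheap to correct.

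**What to change.** - State one rule in both 14.3.13 and 14.3.17: every trial attempted but not finished is scored 180 s, including when both are unfinished. Treat a visit as missing only when the test was not performed for reasons unrelated to walking ability. Define *completed*, or drop the word.
- Analyse the change in walking speed (25 feet divided by the scored time, so 180 s gives about 0.14 ft/s), or use a rank-based method, in place of or alongside raw seconds. State whether speed is taken per trial and averaged, or from the visit mean time. Protocol 8.5.1 and 8.5.3 already leave room for this, and the SAP moved its primary hypothesis tests to the Wilcoxon signed-rank test because of non-normality.
- Report by visit the number of subjects unable to finish one trial, unable to finish both, and excluded for a changed device.

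The cost is SAP wording, a transformation or rank procedure in the program, and one small table. The downside is that speed or ranks are less familiar than seconds; the descriptive medians of raw times already planned would keep that link.
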